4. TRIAL DESIGN

General Design

A multicenter, interventional, randomized comparison of intraoperative hemodynamic management to determine whether use of a protocolized strategy using advanced hemodynamic monitoring with Hypotension Prediction Index (HPI) software guidance for intraoperative hemodynamic management reduces postoperative complication rate in moderate- to high-risk non-cardiac surgery. There will be two arms in this trial, with both arms receiving arterial line monitoring. The treatment arm will receive guidance from a protocolized strategy using advanced hemodynamic monitoring with Hypotension Prediction Index (HPI) software guidance for intraoperative hemodynamic management. The control arm will be blinded to advanced hemodynamic monitoring and will only receive blood pressure monitoring data from the arterial line, as per the standard of care.

A subject will be considered enrolled in the treatment arm once the subject has signed the informed consent and an Acumen IQ sensor has been connected.

A subject will be considered enrolled in the control arm once they signed informed consent and a FloTrac sensor has been connected.

Subjects will be assigned a 6-7-digit Trial Identification Number (Trial ID). The first three-four numbers will identify the site, and the second set of numbers will identify the subject identification number.

For subjects in the treatment arm an Acumen IQ sensor and ForeSight Elite oximetry sensors will be placed prior to the start of the procedure. All advanced hemodynamic parameters including cardiac output (CO), systemic vascular resistance (SVR), stroke volume (SV), stroke volume variation (SVV), Ea_{Dyn} , dP/dt and vital signs will be collected throughout the duration of the procedure and analyzed according to the Statistical Analysis Plan (SAP).

For subjects in the control arm a FloTrac sensor and ForeSight Elite oximetry sensors will be placed prior to the start of the procedure. The control arm will be blinded to advanced hemodynamic monitoring obtained from the FloTrac and ForeSight sensors and will only receive blood pressure monitoring data from the arterial line, as per the standard of care. All vital signs will be collected throughout the duration of the procedure and analyzed according to the SAP.

Subject participation will include preoperative Trial eligibility screening and consent, planned surgical intervention, post intervention follow up through discharge, and 30 days post procedure. Discontinued subject data will be analyzed under intent-to-treat and data will be used for safety and performance analyses.

This Trial will be conducted in a manner that is consistent with the applicable regulations and in accordance with current Good Clinical Practice (GCP).

In accordance with 21 CFR 812.3(m), this Trial does not meet the definition of a significant risk investigation for the following reasons:

- The devices in the treatment arm are being studied in accordance with the indications for use and intended use granted by FDA and therefore are not investigational devices;

THIS DOCUMENT CONTAINS CONFIDENTIAL AND PROPRIETARY INFORMATION OF EDWARDS LIFESCIENCES, LLC. IT MAY NOT BE REPRODUCED OR DISCLOSED WITHOUT PRIOR WRITTEN PERMISSION FROM EDWARDS LIFESCIENCES, LLC.

Edwards Lifesciences, Edwards, the stylized E logo, HemoSphere, Acumen, Acumen IQ, FloTrac, and ForeSight Elite oximetry Sensor are trademarks of Edwards Lifesciences Corporation.

- The devices in the treatment arm are not implants;
- The devices in the treatment arm do not present a potential for serious risk to the health, safety, or welfare of a subject as only subjects requiring an arterial line will be eligible for enrollment in the Trial and;
- The devices in the treatment arm are of substantial importance in diagnosing, mitigating, or treating disease, or otherwise preventing impairment of human health and the general and class II (special) controls provide a reasonable assurance of the safety and effectiveness of adjunctive predictive cardiovascular indicators;
- The Trial relies on the intervention of a learned intermediary prior to initiation of treatment, as the clinicians are utilizing their own clinical judgment in deciding appropriate treatment;
- The HPI Pressure & Flow Optimization Protocol provides recommendations for treatment. Clinicians are instructed to validate the appropriateness of protocol recommendations, and provide treatment based upon their clinical judgment;
- The devices in the treatment arm are not of substantial importance in curing a disease.

[figure not shown]
Treatment Protocol

Subjects assigned to treatment arm will receive treatment per following guidelines:

- Alert Phase: HPI greater than 85 → alert → treatment per protocol recommendation
- Monitoring Phase: HPI 50 – 85 → evaluate flow / vascular tone indices and fluid responsive state.

Figure 1 : Treatment Protocol for Subjects Enrolled in the Treatment Arm

HPI Pressure & Flow Optimization Protocol

Note: Clinicians should validate the appropriateness of protocol recommendations, and provide treatment based upon their clinical judgment.

THIS DOCUMENT CONTAINS CONFIDENTIAL AND PROPRIETARY INFORMATION OF EDWARDS LIFESCIENCES, LLC. IT MAY NOT BE REPRODUCED OR DISCLOSED WITHOUT PRIOR WRITTEN PERMISSION FROM EDWARDS LIFESCIENCES, LLC.

Edwards Lifesciences, Edwards, the stylized E logo, HemoSphere, Acumen, Acumen IQ, FloTrac, and ForeSight Elite oximetry Sensor are trademarks of Edwards Lifesciences Corporation.

Randomization and Blinding

The randomization for this Trial will be implemented using an Interactive Web Response Systems (IWRS). The Sponsor will be blinded to the randomization codes. Participants will be randomized to either the control or treatment arm at enrollment. Study investigators will be blinded up until the time of the surgery. The clinician(s) involved in the consenting of the patient will be blinded to the randomization assignment and will not be involved in the care of the Trial subject. Once the intent of arterial line placement is confirmed with the anesthesia team, before surgery (the day before or in the morning of surgery), the subject will be randomized to either the treatment or control arm. The arterial line will then be placed. Randomization will be allocated in 1:1 ratio, stratified by site.

[figure not shown]
Throughout the Trial, the randomization assignment will remain blinded to all parties, with the study investigators and staff being blinded up until the time to surgery. Randomization assignment can be unblinded in the case of a medical emergency that requires the treatment assignment to be known. In this case, an individual subject blind may be broken via the Code Break Module by the Investigator or Medical Reviewer. When possible, the Investigator is to consult with the Medical Reviewer, or designee, prior to breaking the code. The Investigator is to capture the date, time, and reason for breaking the blind in the subject's source notes. Additionally, an independent biostatistician will be unblinded to the randomization codes in order to conduct the interim analysis. All other parties will be blinded to the randomization at time of the interim. After completion of the Trial, the randomization codes will be unblinded, post database lock and with the Trial Sponsor's approval to unblind.

THIS DOCUMENT CONTAINS CONFIDENTIAL AND PROPRIETARY INFORMATION OF EDWARDS LIFESCIENCES, LLC. IT MAY NOT BE REPRODUCED OR DISCLOSED WITHOUT PRIOR WRITTEN PERMISSION FROM EDWARDS LIFESCIENCES, LLC.

Edwards Lifesciences, Edwards, the stylized E logo, HemoSphere, Acumen, Acumen IQ, FloTrac, and ForeSight Elite oximetry Sensor are trademarks of Edwards Lifesciences Corporation.

[figure not shown]
Schema

Figure 2 Enrollment Flow Diagram

THIS DOCUMENT CONTAINS CONFIDENTIAL AND PROPRIETARY INFORMATION OF EDWARDS LIFESCIENCES, LLC. IT MAY NOT BE REPRODUCED OR DISCLOSED WITHOUT PRIOR WRITTEN PERMISSION FROM EDWARDS LIFESCIENCES, LLC.
Edwards Lifesciences, Edwards, the stylized E logo, HemoSphere, Acumen, Acumen IQ, FloTrac, and ForeSight Elite oximetry Sensor are trademarks of Edwards Lifesciences Corporation.

Figure 3 Enrollment Timeline Diagram

*Roll-ins not included.

THIS DOCUMENT CONTAINS CONFIDENTIAL AND PROPRIETARY INFORMATION OF EDWARDS LIFESCIENCES, LLC. IT MAY NOT BE REPRODUCED OR DISCLOSED WITHOUT PRIOR WRITTEN PERMISSION FROM EDWARDS LIFESCIENCES, LLC.
Edwards Lifesciences, Edwards, the stylized E logo, HemoSphere, Acumen, Acumen IQ, FloTrac, and ForeSight Elite oximetry Sensor are trademarks of Edwards Lifesciences Corporation.

5. SUBJECT CONSENT, SELECTION, AND WITHDRAWAL

General Characteristics of the Proposed Subject Selection

Adults with an ASA classification of ≥ 2 undergoing moderate-to-high-risk noncardiac surgery with expected surgery duration > 2 hours who will be receiving pressure monitoring with an arterial line will be screened for inclusion into the Trial. Only subjects meeting all inclusion criteria will be enrolled. Prior to any Trial procedures, an IRB-approved informed consent form must be signed and dated by the subject or legal guardian. Subjects who have been screened but do not sign an informed consent form will not be considered enrolled and will not have any eCRFs (electronic Case Report Forms) completed.

Informed Consent

Before a subject undergoes any Trial procedures, an informed consent will be obtained utilizing the IRB approved consent form. All consent procedures will be conducted in a manner that is consistent with the applicable regulations and in accordance with Good Clinical Practice (GCP).

During the consent procedure, each potential subject will be given ample time to discuss participation in the Trial and to have any questions or concerns addressed by the Principal Investigator or Investigator. Each subject will be provided with a copy of the IRB approved consent.

Subject Eligibility

All eligible subjects should be screened for Trial eligibility. The Investigator and/or Designee(s) at the Trial site shall review the candidate's eligibility. The Trial site should maintain a cumulative log of all screened subjects in the EDC system.

Inclusion Criteria:

1. Signed informed consent;
2. Age ≥ 18 years;
3. ASA Physical Status ≥ 2 ;
4. Noncardiac surgery with expected surgery duration ≥ 2 hours (example include: orthopedic, spine, urology, and general surgery)
5. Planned blood pressure monitoring with an arterial line catheter;
6. General anesthesia;

THIS DOCUMENT CONTAINS CONFIDENTIAL AND PROPRIETARY INFORMATION OF EDWARDS LIFESCIENCES, LLC. IT MAY NOT BE REPRODUCED OR DISCLOSED WITHOUT PRIOR WRITTEN PERMISSION FROM EDWARDS LIFESCIENCES, LLC.

Edwards Lifesciences, Edwards, the stylized E logo, HemoSphere, Acumen, Acumen IQ, FloTrac, and ForeSight Elite oximetry Sensor are trademarks of Edwards Lifesciences Corporation.

Exclusion Criteria:

1. Participating in another interventional Trial;
2. Contraindication to arterial blood pressure monitoring;
3. Subjects with a physical site area too limited for proper Sensor placement
4. Serum creatine > 175 μ mol/L (>2.0 mg/dL) or CKD stage > 3A
5. Scheduled for intracranial surgery with permissive hypotension;
6. Patient who is confirmed to be pregnant and/or nursing mothers;
7. Patients with an intra-aortic balloon pump (IABP) or ventricular assist device(s);
8. Have a condition that precludes routine or tight blood pressure management such as surgeon request for relative hypotension;
9. Emergency surgery;
10. Require beach-chair positioning;
11. Scheduled for cardiac surgeries
12. Have previously participated in the SMART-BP trial.

THIS DOCUMENT CONTAINS CONFIDENTIAL AND PROPRIETARY INFORMATION OF EDWARDS LIFESCIENCES, LLC. IT MAY NOT BE REPRODUCED OR DISCLOSED WITHOUT PRIOR WRITTEN PERMISSION FROM EDWARDS LIFESCIENCES, LLC.
Edwards Lifesciences, Edwards, the stylized E logo, HemoSphere, Acumen, Acumen IQ, FloTrac, and ForeSight Elite oximetry Sensor are trademarks of Edwards Lifesciences Corporation.

Screen Failures [or Late Screen Failures]

All eligible subjects should be screened for Study eligibility. The Investigator and/or Designee(s) at the Study site shall review the candidate's eligibility. The Trial site should maintain a cumulative log of all screened subjects in the EDC system.

Early Screen Failure

Early Screen Failures are patients who do not meet the inclusion criteria for participation in this trial (screen failure). Patient may be rescreened if they meet inclusion criteria at a later time. Rescreened participants should be assigned the same participant number as for the initial screening.

Late Screen Failure

Late Screen failures are defined as patients who consent to participate in the clinical trial but are not subsequently randomly assigned to the Trial intervention or entered in the Trial.

A Trial ID will be assigned to early screen failures and late screen failures. A minimal set of screen failure information is required to ensure transparent reporting of screen failure participants, to meet the Consolidated Standards of Reporting Trials (CONSORT) publishing requirements and to respond to queries from regulatory authorities. Minimal information includes demographics, screen failure details, and eligibility criteria.

Enrolled Subjects

A subject will be considered enrolled in the Trial once the subject has signed the informed consent, has been assigned a Trial ID, and an arterial line with either a FloTrac sensor (control arm) or Acumen IQ sensor (treatment arm) has been connected. The Trial ID will be a [6-7-digit] number, the first three-four numbers will identify the site, and the second set of numbers will identify the subject identification number.

Roll-in Subjects

In order to avoid a learning curve bias, up to five (5) Roll-in cases may be performed at a site, as needed, with a maximum total of 60 Roll-in cases in the Trial. Roll-in cases will be analyzed separately from the pivotal cohort.

THIS DOCUMENT CONTAINS CONFIDENTIAL AND PROPRIETARY INFORMATION OF EDWARDS LIFESCIENCES, LLC. IT MAY NOT BE REPRODUCED OR DISCLOSED WITHOUT PRIOR WRITTEN PERMISSION FROM EDWARDS LIFESCIENCES, LLC.

Edwards Lifesciences, Edwards, the stylized E logo, HemoSphere, Acumen, Acumen IQ, FloTrac, and ForeSight Elite oximetry Sensor are trademarks of Edwards Lifesciences Corporation.

Early Withdrawal of Subjects

Subjects may voluntarily withdraw consent at any time during the Trial with no loss of benefit or penalty. The Investigator may withdraw any subject if they determine that continued participation in the Trial may be detrimental to the subject's safety and welfare. Subjects withdrawn due to a device complaint or adverse event will be followed through the 30-day telephone follow-up. In addition, if the procedure is aborted early, but after the subject is connected to Trial devices, the subject will be followed for 30 days after the aborted procedure. Each subject withdrawal will be documented on the appropriate eCRF.

Lost to Follow-Up

A participant will be considered lost to follow-up if he or she cannot be reached for the 30-day phone follow-up by the Trial site staff.

The following actions must be taken before a subject is deemed to lost to follow-up:

- The investigator or designee will make every effort to contact with the subject (where possible, three (3) telephone calls and, if necessary, a certified letter to the participant's last known mailing address or local equivalent methods). These contact attempts should be documented in the subject's medical record or electronic Trial Master File (eTMF).
- Should the participant continue to be unreachable, he or she will be considered to have withdrawn from the Trial with a primary reason of lost to follow-up.

6. SCHEDULE OF EVENTS & PROCEDURES

Screening

The study staff will review the subject's medical history for eligibility. Once the potential eligibility has been determined, the study will be discussed with the subject and interest in study participation will be determined. Subjects who fulfill all eligibility criteria will be scheduled for surgery within 30 days of the screening visit.

Pre-Procedure

During the pre-procedure period the following data will be collected:

- Labs:
 - Creatinine
 - Troponin
 - NT-proBNP
- Survey
 - Surgical Risk Assessment (NSQIP)

DAY 1 (DAY OF SURGERY)

On the day of the surgery, clinicians will be asked to follow the recommended treatment protocol for subjects enrolled in the treatment arm to reduce the subject's susceptibility to hypotension, (defined as MAP < 65 mmHg for at least one (1) minute), with guidance for decision support from the Hypotension Prediction Index (HPI) Feature Software. There is no restriction on the type of general anesthesia with or without regional anesthesia administered during the surgery.

The subjects in the treatment arm who are undergoing the planned non-cardiac surgery will have a radial arterial catheter inserted for pressure monitoring. The catheter will be connected to an Acumen IQ sensor and to the HemoSphere advanced monitoring platform with the Hypotension Prediction Index (HPI) Feature Software. The ForeSight Elite oximetry sensors will also be placed on subject's forehead to collect tissue oximetry data for observational purposes.

The subjects enrolled in the control arm will have a radial arterial catheter inserted for pressure monitoring and will have ForeSight Elite oximetry sensors placed on their forehead. The catheter will be connected to a FloTrac sensor and to the HemoSphere advanced monitoring platform, however the clinician will not be able to visualize the HemoSphere advanced monitoring platform and will not have information from FloTrac and ForeSight sensors. The subjects will be treated per standard of care, which includes radial arterial catheter monitoring for blood pressure monitoring.

The study staff may access intraoperative care data from the electronic anesthesia information management system. A designated study staff will be present during the procedures to collect data live. At the completion of the surgery, the hemodynamic monitoring data will be downloaded from HemoSphere advanced monitoring platform.

THIS DOCUMENT CONTAINS CONFIDENTIAL AND PROPRIETARY INFORMATION OF EDWARDS LIFESCIENCES, LLC. IT MAY NOT BE REPRODUCED OR DISCLOSED WITHOUT PRIOR WRITTEN PERMISSION FROM EDWARDS LIFESCIENCES, LLC.

Edwards Lifesciences, Edwards, the stylized E logo, HemoSphere, Acumen, Acumen IQ, FloTrac, and ForeSight Elite oximetry Sensor are trademarks of Edwards Lifesciences Corporation.

DAYS 2-4 (POD 1-3)

The following data will be collected post-operation at Days (POD) 1, 2 & 3:

- Post-Operative Day 1
 - Any fluid and vasoactive medications
 - Obtain post-operative complications
 - Labs: Troponin
 - Post-Op delirium assessment (4AT⁵ or 3D-CAM¹⁷)
- Post-Operative Day 2
 - Obtain post-operative complications
 - Record adverse events
 - Labs: Creatinine and Troponin
 - Post-Op delirium assessment (4AT or 3D-CAM)
- Post-Operative Day 3
 - Obtain post-operative complications
 - Record adverse events
 - Labs: Troponin
 - POMS survey post-operation
 - Post-Op delirium assessment (4AT or 3D-CAM)

If the subject is discharged prior to any of the above schedule of events, a telephone call is sufficient to collect the appropriate required data.

Discharge from the ICU / hospital

The following data will be collected at discharge from the ICU / hospital:

- Obtain post-operative complications
- Record adverse events
- Concomitant Medications: medication that was administered post-operation

30-Day Follow-up

The following data will be collected at 30 days post-procedure via telephone if the subject is no longer in the hospital:

- Obtain post-operative complications
- Record adverse events
- Mortality determination
- WHODAS 2.0 Survey

THIS DOCUMENT CONTAINS CONFIDENTIAL AND PROPRIETARY INFORMATION OF EDWARDS LIFESCIENCES, LLC. IT MAY NOT BE REPRODUCED OR DISCLOSED WITHOUT PRIOR WRITTEN PERMISSION FROM EDWARDS LIFESCIENCES, LLC.

Edwards Lifesciences, Edwards, the stylized E logo, HemoSphere, Acumen, Acumen IQ, FloTrac, and ForeSight Elite oximetry Sensor are trademarks of Edwards Lifesciences Corporation.

Schedule of Events (SoE)

Table 2: Schedule of Events

Trial Procedure / Exam	Subject Screening	Pre-Procedure	Procedure	Post-OP Day 1	Post-OP Day 2	Post-OP Day 3	Discharge	30-Day Follow Up (+14 Days)
Obtain Informed Consent	X							
Perform Inclusion / Exclusion Evaluation	X							
Obtain Medical History / Subject Demographics ¹	X							
Assign Subject ID	X							
Assign Trial Arm	X							
Enter Subject Data into Monitor ³			X					
Vital Signs			X					
Monitoring Duration			X					
Data download from Monitor ³			X					
Obtain Fluid and Vasoactive Medication Administration Record ²			X	X				
Obtain post-operative complications, if applicable			X	X	X	X	X	X
Labs: Creatinine ⁴		X			X			
Labs: Troponin		X		X	X	X		
Labs: NT-proBNP		X						
POMS ⁵						X		
NSQIP Surgical Risk Assessment ⁵		X						
Post-Op delirium assessment (e.g., 4AT or 3D-CAM) ⁵				X	X	X		
WHODAS 2.0 ⁵								X
Complete eCRFs	X	X	X	X	X	X	X	X
Record Adverse Events, if applicable			X	X	X	X	X	X
Obtain ICU / Hospital discharge Information							X	X
Phone Contact 30-day follow up / Mortality Determination								X

¹ Medical History / Subject Demographics / Surgical and Clinician Demographics can be obtained prior to procedure, either at the screening visit or on the day of procedure.

² Can be collected via the hospital record system anytime on the day of procedure or thereafter.

³ To be conducted for subjects assigned to treatment arm

⁴ To be collected on post-op day 1, 2 or 3.

⁵ To be collected if data or subject is available.

THIS DOCUMENT CONTAINS CONFIDENTIAL AND PROPRIETARY INFORMATION OF EDWARDS LIFESCIENCES, LLC. IT MAY NOT BE REPRODUCED OR DISCLOSED WITHOUT PRIOR WRITTEN PERMISSION FROM EDWARDS LIFESCIENCES, LLC.

Edwards Lifesciences, Edwards, the stylized E logo, HemoSphere, Acumen, Acumen IQ, FloTrac, and ForeSight Elite oximetry Sensor are trademarks of Edwards Lifesciences Corporation.

Procedure

The HPI SMART-BP Trial will collect data from up to 1486 subjects at up to 20 study sites across the United States. Up to 60 subjects may be included as roll-ins and will be analyzed separately from the pivotal cohort. Subjects will be randomly assigned to the interventional or control arms. The maximum number of subjects enrolled at each site will not exceed 20% of the total study population.

A subject will be considered enrolled in the Trial once the subject has signed the informed consent, has been assigned a Trial ID, an arterial line with either a FloTrac sensor (control arm) or Acumen IQ sensor (treatment arm) has been connected. Subjects may be screened for eligibility and consented on the day of surgery.

Subject participation will include preoperative study eligibility screening and consent, planned surgical intervention, Post-Op Day 1-3, ICU, hospital discharge, and 30 days post-procedure. Discontinued subject data will be analyzed under intent-to-treat and data will be used for safety and performance analyses.

The subjects enrolled in the treatment arm will have a radial arterial catheter inserted for pressure monitoring and will have ForeSight Elite oximetry sensors placed on their forehead. The catheter will be connected to an Acumen IQ sensor and to the HemoSphere advanced monitoring platform which includes the Acumen™ Hypotension Prediction Index (HPI) feature software. The Acumen HPI software will provide clinicians with information and physiological insight regarding the likelihood of a subject trending towards a hypotensive event (defined as mean arterial pressure \leq 65 mmHg for at least one minute). A secondary screen with associated hemodynamic parameters is available to the clinicians for additional quantitative information regarding the subject's physiological condition. When the Hypotension Prediction Index (HPI) exceeds 85 for two consecutive 20-second updates or reaches 100 at any time, a popup alert will appear on the monitor and clinicians can activate the secondary screen to review all hemodynamic parameters. The anesthesia team will receive a protocolized hemodynamic management strategy and will determine the amount and timing of intravenous fluids and vasopressor or inotropic drugs to be given to subject. Interventions conducted per treatment protocol and/or outside the treatment protocol will be documented on the eCRF(s). Clinicians should validate the appropriateness of protocol recommendations, and provide treatment based upon their clinical judgment.

The subjects enrolled in the control arm will have a radial arterial catheter inserted for pressure monitoring and will have ForeSight Elite oximetry sensors placed on their forehead. The catheter will be connected to a FloTrac sensor and to the HemoSphere advanced monitoring platform; however, the clinician will not be able to visualize the HemoSphere advanced monitoring platform and will not have information from FloTrac and ForeSight sensors. The subjects will be treated per standard of care, which includes radial arterial catheter monitoring for blood pressure monitoring. Patients in the control arm will not have a defined MAP threshold for hypotension and will not receive protocolized hemodynamic management. The anesthesia team will determine the amount and timing of intravenous fluids and vasopressor or inotropic drugs to be given to subject.

THIS DOCUMENT CONTAINS CONFIDENTIAL AND PROPRIETARY INFORMATION OF EDWARDS LIFESCIENCES, LLC. IT MAY NOT BE REPRODUCED OR DISCLOSED WITHOUT PRIOR WRITTEN PERMISSION FROM EDWARDS LIFESCIENCES, LLC.

Edwards Lifesciences, Edwards, the stylized E logo, HemoSphere, Acumen, Acumen IQ, FloTrac, and ForeSight Elite oximetry Sensor are trademarks of Edwards Lifesciences Corporation.

For subjects enrolled in both arms, creatinine values and Surgical Risk Assessment (NSQIP) will be collected during the perioperative period. Troponin values and Post-Op delirium assessment (4AT or 3D-CAM) for POD 1-3, creatinine values for POD 2, POMS survey for POD 3, and 30-day survey will be accessed post operatively.

THIS DOCUMENT CONTAINS CONFIDENTIAL AND PROPRIETARY INFORMATION OF EDWARDS LIFESCIENCES, LLC. IT MAY NOT BE REPRODUCED OR DISCLOSED WITHOUT PRIOR WRITTEN PERMISSION FROM EDWARDS LIFESCIENCES, LLC.
Edwards Lifesciences, Edwards, the stylized E logo, HemoSphere, Acumen, Acumen IQ, FloTrac, and ForeSight Elite oximetry Sensor are trademarks of Edwards Lifesciences Corporation.

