 - f. Mixed effective survival model to assess the multiple event cases within patient
2. Hypotension management analysis
 - a. Time from alert event to intervention
 - b. % alerts with no intervention
 - c. Reasons for nonintervention
 - d. Amount of hypotension removing nonintervention segments
 - e. Agreement analysis; clinical decision vs. treatment algorithm
 - f. Overall treatment protocol compliance
3. Area under the curve AUC MAP under the threshold of 55,65,75 mmHg

THIS DOCUMENT CONTAINS CONFIDENTIAL AND PROPRIETARY INFORMATION OF EDWARDS LIFESCIENCES, LLC. IT MAY NOT BE REPRODUCED OR DISCLOSED WITHOUT PRIOR WRITTEN PERMISSION FROM EDWARDS LIFESCIENCES, LLC.

Edwards Lifesciences, Edwards, the stylized E logo, HemoSphere, Acumen, Acumen IQ, FloTrac, and ForeSight Elite oximetry Sensor are trademarks of Edwards Lifesciences Corporation.

4. Time Weighted Average (TWA) of intraoperative hypotension (mmHg)
5. Time in target SVV <13% (for valid SVV readings = no arrhythmia)
6. Time in target CI >2.5 L/min/m¹⁵
7. Postoperative morbidity survey (POMS) on postoperative day 3
8. Transfusion requirement (mL packed red blood cells)
9. Amounts of intraoperative crystalloid and colloid and vasoactive drugs; mL
10. Amount of vasoactive drugs; mg (e.g.: phenylephrine, ephedrine, norepinephrine, epinephrine, dobutamine)
11. Amount of intraoperative intravenous analgesics and sedatives
12. Brain oxygen saturation – StO₂ using ForeSight Elite tissue oximetry system, time in target
13. Verification of the incidence of the listed postoperative complications may be performed at each site by reviewing historic data up to 6 months prior to study initiation
14. Cost of care
15. Hospital length of stay
16. Hospital readmission within 30 days

Planned Interim Analyses

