16. DATA COLLECTION METHODS

Trial data will be captured utilizing electronic Case Report Forms (eCRFs) including the 30-day follow-up call as well as downloaded files captured directly via the use of the HemoSphere advanced monitor. Data collected from the HemoSphere advanced monitor will be downloaded at the end of each catheterization procedure and stored on a USB stick. USBs will be stored in a secure location at the site, accessible only to Trial site personnel. The HemoSphere data on USBs may be shipped to the Sponsor at any point in time of the Trial per the request of the Sponsor.

THIS DOCUMENT CONTAINS CONFIDENTIAL AND PROPRIETARY INFORMATION OF EDWARDS LIFESCIENCES, LLC. IT MAY NOT BE REPRODUCED OR DISCLOSED WITHOUT PRIOR WRITTEN PERMISSION FROM EDWARDS LIFESCIENCES, LLC.
Edwards Lifesciences, Edwards, the stylized E logo, HemoSphere, Acumen, Acumen IQ, FloTrac, and ForeSight Elite oximetry Sensor are trademarks of Edwards Lifesciences Corporation.

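### Footnote 3 of the Schedule of Events limits monitor set-up and data download to the treatment arm, contradicting the protocol's own download text and the by-arm exploratory analyses in the SAP

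*Combined protocol and SAP*

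**What the plan says.** Table 2 in protocol section 6 marks two procedure-day rows with footnote 3: "Enter Subject Data into Monitor ³" and "Data download from Monitor ³". The footnote reads "To be conducted for subjects assigned to treatment arm". The vital signs and monitoring duration rows carry no such mark.

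The section 6 text for the day of surgery says of control subjects: "The catheter will be connected to a FloTrac sensor and to the HemoSphere advanced monitoring platform". It adds that the clinician cannot see the screen. After describing both arms it says: "At the completion of the surgery, the hemodynamic monitoring data will be downloaded from HemoSphere advanced monitoring platform". No arm is named. Section 16 is broader still: "Data collected from the HemoSphere advanced monitor will be downloaded at the end of each catheterization procedure".

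Protocol section 4 (General Design) treats the arms differently. Under the treatment arm it lists CO, SVR, SV, SVV, Ea_Dyn, dP/dt and vital signs as collected. Under the control arm it lists vital signs only.

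SAP 6.1 names the monitor download as the source of hemodynamic data, and SAP 6.2 expects essentially none of it to be missing. Neither limits this to one arm. SAP 3.2 lists hypotension duration, MAP AUC below 55, 65 and 75 mmHg, TWA of hypotension, and time in target for SVV, CI and StO2. SAP 4.1 presents exploratory analyses by randomized arm, and SAP 8.2 fits treatment-effect models to all the section 3.2 measures.

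**The concern.** The strategy is meant to work by reducing intraoperative hypotension and improving flow, and the protocol's background says that evidence linking less hypotension to better outcome is minimal. A like-for-like comparison of pressure and flow between arms would help explain the primary result, whichever way it falls. Read literally, the schedule tells a site not to download the monitor for controls, although the control sensors and monitor are in place. A coordinator working from the table could reasonably comply, and section 4 would not correct that reading.

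At stake are the exploratory comparisons that rely on monitor data. Some would have no control data. Others would compare monitor data in one arm with some other record in the other, so that a difference in measurement could pass for a treatment effect.

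**Working it through.** This is a check of consistency; the plan gives no figure to reproduce.

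**Step 1. Is the download for one arm or both?**

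| Place | Arms covered |
|---|---|
| Protocol Table 2, footnote 3 | Treatment only |
| Protocol section 4, data collected | Advanced parameters named under treatment only; vital signs under both |
| Protocol section 6, Day 1, download | No limit; follows the description of both arms |
| Protocol section 16, download | No limit; each procedure |
| SAP 6.1 and 6.2, data source | No limit |
| SAP 4.1 and 8.2, analyses of SAP 3.2 measures | Both arms needed |

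The first two places point to no control download. The others describe or require one. The documents do not say which prevails.

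**Step 2. What happens to each measure if the footnote is followed?**

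| Measure in SAP 3.2 | Control-arm position |
|---|---|
| Time in target, SVV | No identified source |
| Time in target, CI | No identified source |
| Time in target, StO2 | No identified source |
| TWA of hypotension | Not computable as written: the denominator in SAP 12.3 runs from first to last valid monitor time |
| MAP AUC below 55, 65, 75 mmHg | Possible from vital signs or the anesthesia record, so a different source from the treatment arm |
| Hypotension duration | As for AUC |

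So 3 measures have no identified control source, 1 cannot be computed as specified, and 2 rest on unlike sources: 3 + 1 + 2 = 6. SAP 12.3 calls the monitor EV1000, which is not in the protocol's device list. I take it to mean the trial monitor.

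**Step 3. Does the source matter for pressure?** SAP 3.2 defines an episode as MAP below 65 lasting at least 1 minute, and SAP 8.4 varies that duration to 20, 40 and 80 seconds. Such definitions depend on how often pressure is recorded. The protocol refers to 20-second HPI updates on the monitor; no interval is given for control vital signs or the anesthesia record.

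**Step 4. Do the missing-data rules help?** SAP 6.2 carries the last monitor value forward. A subject with no download has no value to carry. SAP 6.2 also defines missing data as collection attempted and failed. A download omitted under the footnote was never attempted, so it falls outside that definition.

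**Step 5. How many controls?** The protocol's pivotal sample is 1426, which agrees with the SAP total less roll-ins: 1486 − 60 = 1426. With 1:1 allocation, 1426 / 2 = 713 controls are exposed if every site follows the footnote.

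**Step 6. Is the primary test affected?** SAP 8.1 compares proportions with the 30-day composite. It uses no monitor data.

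**The case against.** The best defence is that the intention is clear from the rest of the plan. Controls wear the sensors and are connected to the monitor, section 16 covers every procedure, and the SAP expects the data to be there. On that view the footnote is a slip. This has force, and it is why a reader who infers that the trial will have no control hemodynamic data goes too far: that follows only if the footnote overrides the text. But section 4 supports the footnote, so the slip is not self-evident.

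A second defence is that control pressure is recorded anyway. Vital signs are collected throughout the procedure, study staff may consult the electronic anesthesia record, and a staff member is present to collect data live. This stands for arterial pressure. A reader might infer that all six measures would exist in one arm only, and that is not supported for AUC or duration. It does not rescue SVV, CI or StO2: no document says that anyone records these live from the hidden control monitor.

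A third defence is that tissue oximetry is included for observation only. That concerns its use in care. SAP 3.2 and 8.2 still plan a treatment comparison of StO2.

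Two other inferences are tempting. One is that the primary result could not be interpreted. The primary test evaluates the strategy on clinical outcomes and stands without these data; only the explanation of the result is weakened. The other is that data not downloaded at the end of a case are lost for good. The documents do not describe how long the monitor keeps data, so this cannot be asserted.

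**Conclusion.** The point holds as an internal contradiction. It does not establish that control data will be lost. Footnote 3, with section 4 leaning the same way, conflicts with protocol sections 6 and 16, with SAP 6.1 and 6.2, and with the planned by-arm models. Where the footnote is followed, three exploratory measures have no identified control source, one cannot be computed as written, and two compare unlike sources. The upper limit is 713 controls, assuming the planned pivotal size and every site complying; the number at any one site depends on which text its staff follow. Where sections 6 and 16 are followed instead, the data exist for all six measures. The affected measures are all exploratory, and neither the primary analysis nor the sample size changes. It should be corrected, because the planned comparisons need the data and the equipment is already in place.

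**What to change.** 1. Delete footnote 3 from both Table 2 rows, or reword it to say that the step applies to both arms, with the screen not visible to the clinician in the control arm.
2. Align the control-arm sentence in protocol section 4 so that it lists the hidden FloTrac and ForeSight data as collected. Correcting the footnote alone would leave this conflict in place.
3. State in the SAP that MAP-based measures (AUC, TWA, duration) use the HemoSphere download at the same sampling interval in both arms, and name that monitor in the TWA formula.
4. If any control cases have already been run without a download, ask sites whether the data can still be retrieved, and report the number of subjects with monitor data by arm.

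The cost is a footnote, a sentence in section 4, a short SAP clarification and a memo to sites, plus the time to download each control case. No new equipment is needed. The earlier it is done, the fewer control cases are affected.
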